## 9.2 Other Analyses

### 9.2.1 Secondary Endpoints Assessing Ordinal Scale Status

The area under the curve (AUC) over time for a given subject will be calculated (using the linear trapezoidal rule) as the sum of the maximum ordinal score for each day up through Day 7 and Day 14. An analysis of treatment group differences will be performed on these per-subject AUC values using analysis of variance, with treatment group and randomization strata as fixed factors. A sensitivity analysis will be performed that excludes the category of death on study, to determine if death as an outcome skews the results; death as an outcome will also be analyzed as an independent secondary endpoint using all available death information.

A secondary analysis of treatment group effect on the difference in proportions of subjects with the worst (death) versus the best outcome (discharge from hospital and resumption of normal activities) will also be performed. This analysis does not use scores for the ordinal outcome but does account for ordinality and is therefore not dependent on the relationship of score to severity of outcome. P-values will be based on logistic regression treatment comparisons of best vs. worst vs. other categories adjusting for randomization strata.

An exploratory analysis will be performed through an exact categorical analysis of treatment group differences in the ordinal scale results using the worst outcome across all assessments on a per-subject basis.

Additional ordinal scale outcome assessments will include comparison of total numbers of days up to and including Day 14 at more severe scale values (death, time on ventilator, time in ICU) and proportions of subjects with ordinal scale worsening post enrollment.

Using the modified ordinal scale described in Table 2, frequency analyses by visit, AUC analyses (up to Day 7 and up to Day 14) and best versus worst versus other analyses will also be generated.

Proportion outcomes will be analyzed by categorical data analysis methods, including logistic regression adjusted for strata. Additional exploratory subgroup analyses may also be performed, for example, based on various age categories or other subgroup variables. Time from onset of symptoms to study treatment and the number of doses of oseltamivir (Tamiflu) prior to VIS410 treatment for the current case of influenza may be included as covariates in the analyses.

Clinical Outcome	Score
Death	5
ICU stay with mechanical ventilation	4
ICU stay without mechanical ventilation	3
Non-ICU hospitalization	2

Discharge	1
-----------	---

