The area under the curve (AUC) over time for a given patient will be calculated as the sum of the maximum ordinal score for each day up through 7 and 14 days. An analysis of treatment group differences will be performed on these per-patient AUC values using analysis of variance, with treatment group and strata as fixed factors. A sensitivity analysis will be performed that excludes the category of death on study, to determine if death as an outcome skews the results; death as an outcome will also be analyzed as an independent secondary endpoint. A secondary analysis of treatment group effect on the difference in proportions of patients with the worst (death) versus the best outcome (discharge from hospital and resumption of normal activities) will also be performed. This analysis does not use scores for the ordinal outcome but does account for ordinality, and is therefore not dependent on the relationship of score to severity of outcome. An exploratory analysis will be performed through an exact categorical analysis of treatment group difference in the ordinal scale results using the worst outcome on a per-patient basis.

Additional ordinal scale outcome assessments will include comparison of total numbers of days at more severe scale values (death, time on ventilator, time in ICU) and proportions of patients with ordinal scale worsening post enrollment. Proportion outcomes will be analyzed by categorical data analysis methods, including Mantel-Haenszel chi-square tests adjusted for strata; additional exploratory subgroup analyses may also be performed, for example, based on various age categories. Time from onset of symptoms to study treatment and the number of doses of oseltamivir (Tamiflu) prior to VIS410 treatment for the current case of influenza may be included as covariates in the analyses.

Secondary and exploratory endpoints will be analyzed for descriptive purposes, with significance levels (p-values) provided to illustrate the strength of evidence for treatment effects, and to provide a basis for the choice of endpoints for further study in a confirmatory study. These analyses will also provide estimates for potentially powering additional efficacy endpoints, and to assist in hierarchical ordering of secondary endpoints to provide alpha-control in confirmatory studies and for labelling purposes.

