  - Geographic region of enrollment
- Time to clinical response defined as resolution of at least 4 of 5 vital signs
  - Afebrile with core temperature ≤ 37.8°C, without use of antipyretics (oral ≤ 37.2°C)
  - Oxygen saturation ≥ 95% on room air without support or a return to pre-infection status, if pre-infection status was < 95%
  - Pulse rate ≤ 100/min
  - Systolic blood pressure ≥ 90 mm/Hg, without vasopressor use
  - Respiratory rate ≤ 24 beats per minute
- Clinical status ordinal scale mean area under curve for Days 1-7 and Days 1-14, using linear numeric scores for the ordinal categories.
- Comparison of clinical status ordinal scale scores for selected individual days (ie, Days 3, 4, 5, and 6)
- Comparison of clinical status ordinal scale scores using modified ordinal scale criteria (ie, pooling of selected severity criteria scores)
- Comparison of discrete ordinal scale parameters, including days of ventilator support, days in intensive care, and duration of hospitalization
- Number of days to resumption of usual activities
- All-cause and attributable mortality rates at Day 14, 28 and 56
- Total number of days in hospital and/or intensive care unit (ICU) from admission to discharge and rate of rehospitalization due to influenza A relapse/complication
- The incidence, severity, and duration of signs and symptoms of influenza-like illness as assessed by the FluPRO Questionnaire (see Appendix 16.3.1)
- The percentage of subjects with new bacterial pneumonia/superinfection

January 17, 2019

- The percentage of subjects with influenza-related complications
- VIS410 pharmacokinetic (PK) parameters in serum
- Titer of anti-VIS410 antibody positive samples
- Genotypic and/or phenotypic assessment to determine the emergence of VIS410 and oseltamivir-resistant viruses

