### **9.1 Primary Efficacy Analysis – Day 7 Ordinal Scale Status**

The ordinal scale outcomes will be measured daily from Day 1 (Baseline) through Day 14 using the seven-level hierarchical scale with the classifications presented in the table below. The clinical outcomes therein are ordered from the worst clinical outcome to the best clinical outcome in descending order. For each day, subjects will be classified by the worst clinical

January 17, 2019

outcome for which they qualify. The number and percentage of subjects in each treatment group with each classification will be summarized for each day from Day 1 through Day 14, inclusive. For subjects who die prior to Day 7, the score of 7 will be carried forward through Day 14. If a subject is missing an ordinal scale value but is bracketed by the same values on immediately preceding and subsequent days, the value of the missing day will be imputed to be the same as the immediately preceding and subsequent days. If a subject is missing baseline ordinal scale values from Day 1, baseline values will be set to the Day 2 score. If subjects are missing Day 1 and Day 2, the baseline value will not be imputed. No other data will be imputed.

Clinical Outcome	Score
Death	7
ICU stay with mechanical ventilation	6
ICU stay without mechanical ventilation	5
Non-ICU hospitalization with supplemental oxygen	4
Non-ICU hospitalization without supplemental oxygen	3
Discharge with partial resumption of normal activities	2
Discharge with full resumption of normal activities	1

For use in overall summary statistical presentations, the ordinal categories will be assigned decreasing integer scores, with death a score of 7 and discharge with full resumption of normal activities a score of 1. Frequencies of ordinal scores at each visit will be generated and evaluated by proportional odds ratio analysis, as implemented by logistic regression, including a test of the proportional odds assumption and generation of common odds ratios. For this analysis, the reference response category will be 1= Discharge with full resumption of normal activities with the remaining response categories in numeric sequence to worst (7=Death). Additional exploratory analyses may be conducted to obtain a more complete understanding of the relationship of treatment to the ordinal response.

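### The ordinal-scale AUC is given two different formulas, and the SAP does not say how it is computed when days are missing after withdrawal, at the end of follow-up, or after a death on Day 7 or later

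*SAP*

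**What the plan says.** The endpoint list in SAP 3.2 names "Clinical status ordinal scale mean area under curve for Days 1-7 and Days 1-14". SAP 9.2.1 computes it "using the linear trapezoidal rule) as the sum of the maximum ordinal score for each day up through Day 7" and Day 14, and compares the per-subject values by ANOVA with treatment and randomization stratum as factors. The efficacy part of the protocol synopsis has a plain sum, "calculated as the sum of the maximum ordinal score for each day up through 7 and 14 days", with no trapezoid. SAP 16.1, which lists changes from the protocol analyses, does not mention the difference.

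The SAP scale gives "death a score of 7 and discharge with full resumption of normal activities a score of 1", so a lower AUC is better.

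SAP 9.1 has three rules for missing daily scores:

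- A gap is filled under this condition: "If a subject is missing an ordinal scale value but is bracketed by the same values on immediately preceding and subsequent days".
- For baseline: "If a subject is missing baseline ordinal scale values from Day 1, baseline values will be set to the Day 2 score".
- For deaths: "For subjects who die prior to Day 7, the score of 7 will be carried forward through Day 14".

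It then closes the list: "No other data will be imputed". SAP 4.2 leaves missing data as missing by default. Protocol 10.5 left the method to the SAP and named carry-forward and interpolation as possibilities.

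**The concern.** An AUC that is not divided by time depends on how many days enter it. On this scale every recorded day adds at least 1, so a day that adds nothing counts as better than full recovery. Whoever programs the endpoint must decide what to do with an incomplete course, and the SAP does not decide it.

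Missing days are foreseeable. The scale is due daily to Day 14, but discharged subjects have outpatient visits only on Days 3, 5, 7 and 14 (Protocol 4.1), and the diary contents in Protocol 8.4 do not include the ordinal scale. Subjects can also leave while ill: Protocol 10.2 requires withdrawal after an investigator breaks the code, and Protocol 11.3 does not replace withdrawn subjects.

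The stakes go beyond one table. The study intends to use p-values to choose Phase 3 endpoints (SAP 2.2). The same AUC also feeds the death-excluded analysis, the five-level modified scale and the ICU sensitivity analysis.

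**Working it through.** The plan states no AUC value, standard deviation or dropout rate, so there is no figure to reproduce. The score sequences below are assumptions on the SAP's 1–7 scale. Recoverers start at 4 because oxygen support is an entry criterion.

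**1. Sum against trapezoid, complete data.** For daily scores S1 to Sk, trapezoid = sum − (S1 + Sk)/2. For 4,4,4,3,3,2,2 the sum is 22 and the trapezoid is 22 − (4 + 2)/2 = 19.

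**2. Interior gap between unequal scores.** Take 4,4,missing,2,2,1,1. The SAP 9.1 rule does not fill it.
- Sum of available days: 14, against 17 had a 3 been recorded.
- Trapezoid using actual days: 4 + (4 + 2)/2 × 2 + 2 + 1.5 + 1 = 14.5, the same as with the 3 recorded.

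The choice of formula therefore decides whether interior gaps matter. A gap of several days is also left unfilled by SAP 9.1, because the rule needs values on the immediately adjacent days.

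**3. Early departure while ill, if available days are totalled.** Score 6 on Days 1–3, then missing:
- Sum 6 × 3 = 18 and trapezoid 18 − 6 = 12, against 22 and 19 for the recoverer in step 1.
- Mean per recorded day: 18/3 = 6.0 against 22/7 = 3.14, so the ordering is reversed.
- With the last score carried forward to Day 7: sum 6 × 7 = 42 and trapezoid 36, which restores the order.

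**4. How early the departure must be.** Under the sum, with a score of 6 until departure:

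| Recoverer, Days 1–7 then 8–14 | Day 7 sum | Leaver lower if last seen by | Day 14 sum | Leaver lower if last seen by |
|---|---|---|---|---|
| Fast: 4,4,3,2,2,1,1 then all 1 | 17 | Day 2 | 24 | Day 3 |
| Typical: 4,4,4,3,2,2,2 then 2,2,2,1,1,1,1 | 21 | Day 3 | 31 | Day 5 |
| Slow: 4,4,4,4,4,3,3 then 2,2,2,2,1,1,1 | 26 | Day 4 | 37 | Day 6 |

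A leaver last seen on Day 5 has 6 × 5 = 30, worse than all three recoverers at Day 7.

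**5. Death after the carry-forward cut-off.** Ventilated on Days 1–7, death on Day 8:
- Without carry-forward, the Day 14 sum is 6 × 7 + 7 = 49.
- With carry-forward it is 49 + 7 × 6 = 91.
- A survivor with ten ventilated days and four ICU days has 6 × 10 + 5 × 4 = 80, so the uncarried death ranks better than that survivor.

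**6. The alternative reading.** If an incomplete AUC is set to missing, steps 3 and 5 produce no reversal, but those subjects drop out of the ANOVA.

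**The case against.** SAP 9.1 does contain rules for missing days, and one of them covers deaths before Day 7, a main way in which a very ill subject's scores stop early. A reader might infer that the plan has no missing-day rule at all. That would be wrong; the gap is in what the three rules leave out.

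The SAP nowhere says that missing days add nothing. Leaving data missing is equally compatible with dropping the subject, and then no one receives a flattering AUC. This stands: the reversal is a consequence of one reading, and even then it needs early departure.

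The trapezoid, as SAP 9.2.6 writes it out for FluPRO with interval weights, bridges interior gaps. If Day 14 is recorded, unrecorded days between discharge and Day 14 would be interpolated. This also stands, and it limits the trapezoid problem to days after the last recorded score. It does not settle the matter, because the same SAP sentence also says sum and the protocol says only sum.

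The word mean in the endpoint name may simply refer to the group mean of per-subject AUCs. That is a fair reading, so the name is ambiguous and not a contradiction.

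Finally, the study is exploratory and unpowered, its p-values are for information only, and the Day 7 primary analysis does not use the AUC. This lowers the severity but does not remove the ambiguity.

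**Conclusion.** The concern holds as a gap in specification with real consequences. The formula is ambiguous even for complete data. Three kinds of missing day are uncovered under either formula: after a living subject withdraws, trailing unrecorded days after discharge, and after a death on Day 7 or later. Under the plain sum, gaps between unequal scores and gaps of several days are uncovered as well. Depending on an unstated choice, the result is either AUCs that can rank an early, very ill leaver or a later death too favourably, or the loss of sick subjects from the comparison.

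Two stronger conclusions are tempting and unsupported. One is that a sick leaver necessarily scores better than a recoverer. In the illustrative courses this needs partial summing and a last recorded day no later than about Day 2–4 for the Day 7 AUC, or Day 3–6 for the Day 14 AUC. The other is that any imbalance in missing days favours the arm with more of them. That fails if interior gaps are bridged or incomplete subjects are dropped. With no missingness rate in either document, neither the size nor the direction of bias between arms can be computed.

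Severity: moderate.

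**What to change.** Amend SAP 9.2.1 before unblinding:

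1. Choose one formula. The trapezoid as written out in SAP 9.2.6 would serve, since it interpolates interior gaps. If a mean is intended, divide by the fixed window length: 6 days for Days 1–7 and 13 for Days 1–14. The recoverer in step 1 would score 19/6 = 3.17.
2. Carry the score of 7 through Day 14 for every death up to Day 14.
3. State how days after withdrawal or after the last recorded score are filled, by last score carried forward or by multiple imputation.
4. Report AUC per observed day, or complete cases, as a sensitivity analysis only. Dividing by observed days alone penalises early leavers: a course of 4,4,4,4,3,3,2 averages 24/7 = 3.43, but cut after Day 2 it averages 4.0.
5. Apply the same rules to the death-excluded, five-level and ICU-sensitivity AUCs where they are relevant, and record the change in SAP 16.1.

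The cost is a few sentences, modest programming and an imputation assumption that must be stated and defended.

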## 2 STUDY DESIGN AND OBJECTIVES

### 2.1 Trial Design

This is a Phase 2b, multicenter, randomized, double-blind, controlled study comparing the efficacy and safety of 2 dose levels of VIS410 (2000 and 4000 mg) in combination with oseltamivir vs oseltamivir alone in hospitalized subjects with influenza A infection requiring oxygen support. Subjects will be randomly assigned at a ratio of 1:1:1 using a permuted block randomization method to receive VIS410 at a dose of 2000 mg (low dose) or 4000 mg (high dose) or placebo (0.9% sodium chloride), administered as a single IV infusion over 2 hours. Randomization will be stratified by presence or absence of positive pressure ventilation (PPV) at baseline to ensure an even distribution across treatment arms. All subjects will receive oseltamivir 75 mg twice daily (BID) for 5 days (total of 10 doses) as part of standard of care. Treatment with oseltamivir may be extended for up to 5 additional days (up to 20 doses of total therapy) if clinical symptoms warrant further treatment as assessed by the Investigator. Depending on standard of care, subjects may have started oseltamivir therapy prior to randomization. All subjects will also receive a pretreatment regimen of diphenhydramine 50 mg PO or IV plus either ibuprofen 400 mg PO or acetylsalicylic acid 320-325 mg PO approximately 60 minutes before infusion. Approximately 120 evaluable subjects (40/arm) with confirmed influenza A infection will be treated.

Study assessments are outlined in the Schedule of Assessments (copy in Appendix 16.2). Subjects discharged from the hospital prior to Day 14 will attend the applicable out subject follow-up visit(s) (e.g., Day 3, Day 5, Day 7, Day 14) per Table 1. The total study duration for each subject (screening through study exit) will be approximately 8 weeks (Day 56).

January 17, 2019

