If it is determined that the level of care provided for particular subjects was driven by factors other than subject disease severity and acuity, data from these subjects will be analyzed in sensitivity analyses. Sensitivity analyses will be generated for ordinal score frequencies, AUC (baseline to Day 7 and to Day 14), post-baseline ordinal scale worsening and days in ICU. These sensitivity analyses will utilize updated ordinal scale measures based on data provided by investigators for subjects who remained in the ICU for reasons other than disease severity (for example, lack of non-ICU beds available). This information will be captured in a spreadsheet that will be locked and signed prior to database lock.

If the conclusions from the primary analysis of the Seven-Level Ordinal Scale differ from those resulting from the above sensitivity analyses, additional exploratory analyses will be performed. These analyses include but are not limited to assessments of whether the analysis conclusions

January 17, 2019

differ only at certain sites or whether the differences in the results remain after adjusting for covariates related to site, disease severity or other factors potentially related to outcome.

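### The ordinal AUC model leaves out the baseline ordinal score, and the worst-outcome analysis counts that score as outcome: modest precision is lost in the first, and recovery cannot show in the second

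*SAP*

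**What the plan says.** SAP 9.1 has the ordinal scale "measured daily from Day 1 (Baseline) through Day 14", so the Day 1 score is the baseline score.

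That score enters two analyses in SAP 9.2.1:

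- **AUC.** It is calculated "as the sum of the maximum ordinal score for each day up through Day 7 and Day 14". SAP 3.2 lists it as "Clinical status ordinal scale mean area under curve for Days 1-7 and Days 1-14", and the sensitivity analyses in SAP 9.1 describe it as "AUC (baseline to Day 7 and to Day 14". Treatment groups are compared "using analysis of variance, with treatment group and randomization strata as fixed factors".
- **Worst outcome.** An exploratory exact analysis compares groups "using the worst outcome across all assessments on a per-subject basis". Day 1 is not excluded and no covariate is named.

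The strata come from SAP 2.1: "Randomization will be stratified by presence or absence of positive pressure ventilation (PPV) at baseline". SAP 9.2.1 also allows two optional covariates, time since symptom onset and number of prior oseltamivir doses. The baseline ordinal score is not among them. For viral load AUC, by contrast, SAP 9.2.8 plans baseline-adjusted comparisons and a possible ANCOVA with baseline as a continuous covariate.

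**The concern.** Subjects enter because they need oxygen support (Protocol 5.2.1, criterion 4), so most are at or near their worst on Day 1. A baseline value that is carried in the outcome and left out of the model adds between-subject variation that treatment cannot influence.

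This matters more here than in most exploratory trials. SAP 2.2 says that significance testing will be used to judge the relative strength of evidence of the endpoints, in order to choose candidates for Phase 3. With about 40 subjects per arm, an endpoint that carries removable noise may be ranked lower than it deserves.

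**Working it through.** **Is there a figure to reproduce?** No. The current documents give no SD, effect size, power or baseline-outcome correlation for the ordinal AUC. Every size below therefore rests on assumptions.

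**What the PPV stratum leaves unadjusted.** PPV covers invasive and noninvasive ventilation (Protocol 10.2), so the stratum takes up most of the contrast between score 6 and lower scores. Among subjects without PPV, 4 versus 5 remains.

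**Does it matter that Day 1 is in the sum?** Little. SAP 9.2.1 calls the AUC both a trapezoid and a sum. Day 1 has weight 1/2 under the first and 1 under the second, so it counts either way. Once the Day 1 score is a covariate, the Days 1-7 sum is the Days 2-7 sum plus a term already in the model, and the treatment test is identical. The missing covariate is the issue.

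**Value of the covariate.** The gain in effective sample size is (residual SD with PPV only / residual SD with PPV and baseline score)², which equals 1/(1 - r²), where r is the baseline-AUC correlation after PPV.

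*Simulation 1.* Assumptions: at baseline 65-80% on ward oxygen, 10-20% in ICU without ventilation and 10-15% ventilated (taken as the PPV stratum); each day a 25-35% chance of stepping down one level and 4-8% of stepping up one; death absorbing. I ran 16 combinations with 200,000 subjects each. The extremes were:

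| Baseline mix (4/5/6), daily down/up | AUC | SD, PPV only | SD, plus baseline | Ratio squared |
|---|---|---|---|---|
| 80/10/10%, 35%/8% | Days 1-7 | 5.889 | 5.519 | 1.14 |
| 70/20/10%, 25%/4% | Days 1-7 | 5.422 | 4.680 | 1.34 |
| 80/10/10%, 35%/8% | Days 1-14 | 13.890 | 13.442 | 1.07 |
| 70/20/10%, 25%/4% | Days 1-14 | 13.260 | 12.275 | 1.17 |

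The gain is 14-34% for Days 1-7 and 7-17% for Days 1-14.

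*Simulation 2, different assumptions.* 80 pooled VIS410 versus 40 placebo; 10-25% on PPV; 15-45% of the rest in ICU; step rates that depend on the current level; between-subject variation in recovery; a treatment effect on both step rates; 2,000 trials per scenario.

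- Days 1-7: r was 0.35-0.49, so 1/(1 - 0.35²) = 1.14 to 1/(1 - 0.49²) = 1.32. Power rose from 38-42% to 45-48%, about 5-9 points.
- Days 1-14: r was 0.24-0.35, so 1/(1 - 0.24²) = 1.06 to 1/(1 - 0.35²) = 1.14. Power rose from 46-48% to 48-53%, about 2-5 points.
- Dropping Day 1 from the Days 1-7 sum without adding the covariate gained only 1-2 points.

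**Worst outcome.** With every subject on oxygen support, Day 1 sets a floor of about 4. A subject who goes home on Day 3 and one who stays on ward oxygen for two weeks both score 4. Only deterioration above the Day 1 level can separate the arms. In simulation 1 the worst score over Days 1-14 equalled the Day 1 score in 71-89% of subjects. In simulation 2 the share was 84-86%. Using a Mann-Whitney test as a stand-in for the exact test, power in simulation 2 was 8-11% with Day 1 counted and 16-22% with post-baseline days only.

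**The case against.** The strongest reply is that little is at stake. The ANOVA is valid, PPV already captures most of the severity contrast, the worst-outcome analysis is labelled exploratory, and SAP 4.1 gives p-values for information only. SAP 9.2.1 also plans a comparison of the proportions who worsen after enrollment, which uses change from baseline directly. SAP 9.1 allows adjustment for disease severity in further exploratory work.

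Much of this stands. The loss for the AUC is modest, especially over Days 1-14, and the worsening comparison partly covers what the worst-outcome analysis would miss. But that comparison does not make the AUC more precise. The severity adjustment is triggered only if the primary and sensitivity conclusions differ. And exploratory status is a weak defence when ranking endpoints is the trial's stated purpose.

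A second reply also stands: the Day 1 score as recorded is not a clean baseline. SAP 9.1 replaces a missing Day 1 score with the Day 2 score, which follows the infusion, and it classifies Day 1 by the worst status of the whole day. SAP 4.1 defines baseline as the last value before study drug. The covariate must respect that definition.

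A reader might infer that the planned AUC analysis is biased or conceals a treatment effect. The documents do not support that. Treatment is randomized within PPV strata, so baseline severity is balanced in expectation and the cost is precision only.

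**Conclusion.** The point holds as one of efficiency for the AUC and of construction for the worst-outcome analysis. For the AUC, leaving out the baseline ordinal score costs the equivalent of roughly 14-34% more subjects over Days 1-7 and 7-17% over Days 1-14. The Days 1-7 figure should not be applied to Days 1-14, where baseline carries less weight. In the exploratory worst-outcome analysis, about 71-89% of subjects would simply contribute their Day 1 status.

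The textual facts are certain. The sizes depend on assumed baseline mixes and transition rates and would change with the enrolled population. The primary Day 7 analysis is not affected by this point.

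**What to change.** In SAP 9.2.1:

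1. **AUC.** Add the baseline ordinal score as a covariate alongside the PPV stratum, for both the seven-level and five-level scales. Day 1 may stay in the sum.
2. **Covariate definition.** Use pre-infusion status, consistent with SAP 4.1. Where Day 1 is missing, do not use the Day 2 score as the covariate; use, for example, the screening or pre-dose level of care. Ventilation times and ICU dates are already recorded (Protocol 6.3.3 and 6.3.5). Because Protocol 6.3.5 names ICU dates and not clock times, state a rule for an ICU admission dated Day 1.
3. **Worst outcome.** Take the worst score over Days 2-14, stratify the exact analysis by baseline score, and show Day 1 only as baseline. Stratification is needed because in simulation 1 the worst score over Days 2-14 still equalled the Day 1 score in 51-64% of subjects.

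The cost is SAP wording and minor programming, with no new data.

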## 16.6 List of Proposed Tables, Figures, and Listings

### 16.6.1 Tables

Table	Title	Population
14.1.1.1	Subject Disposition	ITT
14.1.1.2	Subject Disposition	MITT
14.1.1.3	Subject Disposition by Region and Site	ITT
14.1.2.1	Summary of Protocol Deviations	ITT
14.1.3.1	Demographics and Baseline Characteristics	ITT
14.1.3.2	Demographics and Baseline Characteristics	MITT
14.1.4.1	Medical History	ITT
14.1.4.2	Medical History	MITT
14.1.5.1	Prior Medications	ITT
14.1.5.2	Prior Medications	MITT
14.1.6.1	Concomitant Medications	Safety
14.1.7.1	Treatment Exposure and Compliance	Safety
14.1.7.2	Treatment Exposure and Compliance	MITT
14.2.1.1.1	Summary of Clinical Outcome on Seven-Level Ordinal Scale through Day 14	MITT
14.2.1.1.2	Summary of Clinical Outcome on Five-Level Modified Ordinal Scale through Day 14	MITT
14.2.1.1.3	Summary of Clinical Outcome on Seven-Level Ordinal Scale through Day 14 Sensitivity Analysis	MITT
14.2.1.2	Summary of Area Under the Curve for Seven-Level Ordinal Scale	MITT
14.2.1.3	Summary of Area Under the Curve for Seven-Level Ordinal Scale Excluding Death Outcome	MITT
14.2.1.4	Summary of Area Under the Curve based on Modified Five-Level Ordinal Scale	MITT
14.2.1.5	Summary of Area Under the Curve for Seven-Level Ordinal Scale Sensitivity Analysis	MITT
14.2.1.6	Additional Assessments for Seven-Level Ordinal Scale	MITT
14.2.1.7	Additional Assessments for Seven-Level Ordinal Scale Sensitivity Analysis	MITT
14.2.1.8	Summary of Proportions of Best and Worst Cases for Seven-Level and Modified Five-Level Ordinal Scale	MITT
14.2.2.1	Time to Cessation of O2 Support	MITT
14.2.3.1.1	Kaplan-Meier Estimates of Time to Clinical Response (Resolution of Vital Signs)	MITT
14.2.3.1.2	Kaplan-Meier Estimates of Time to Clinical Response (Resolution of Vital Signs) in Subjects with > 2 Vital Sign Abnormalities at Baseline	MITT

14.2.3.1.3	Kaplan-Meier Estimates of Time to Complete Clinical Response (Resolution of Vital Signs)	MITT
14.2.3.1.4	Kaplan-Meier Estimates of Time to Complete Clinical Response (Resolution of Vital Signs) in Subjects with >2 Vital Sign Abnormalities at Baseline	MITT
14.2.4.1	Kaplan-Meier Estimates of Time to Cessation of Ventilator Support	MITT
14.2.5.1	Summary of Healthcare Resource Utilization Parameters	MITT
14.2.5.2	Summary of Visual Analogue Scale Scores	MITT
14.2.6.1.1	Descriptive Summary of FluPRO Domain Scores, Component Scores, and Total Score	MITT

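### The AUC sensitivity analysis that excludes death does not say how death is removed, and both natural readings favor the arm with more deaths

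*SAP*

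**What the plan says.** SAP 9.2.1 computes a per-subject AUC "as the sum of the maximum ordinal score for each day up through Day 7 and Day 14" and compares arms "using analysis of variance, with treatment group and randomization strata as fixed factors". The scale runs upward with severity, "with death a score of 7 and discharge with full resumption of normal activities a score of 1" (SAP 9.1). The section then adds: "A sensitivity analysis will be performed that excludes the category of death on study, to determine if death as an outcome skews the results". The efficacy part of the protocol synopsis has the same instruction, "A sensitivity analysis will be performed that excludes the category of death on study", and the output is Table 14.2.1.3, "Summary of Area Under the Curve for Seven-Level Ordinal Scale Excluding Death Outcome". None of these places says what is removed, and none rescales the AUC for subjects with fewer scored days. On the handling of death in general, SAP 9.1 states "For subjects who die prior to Day 7, the score of 7 will be carried forward through Day 14", followed after two narrow imputation rules by "No other data will be imputed". Section 9.2.1 also plans a separate analysis of death as a secondary endpoint.

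**The concern.** The purpose is to learn whether the weight given to death drives the AUC comparison. Taking death out of an unscaled sum does not answer that.

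- If death days are left out, a subject who dies early contributes only a few scored days, and a short sum looks like a good outcome.
- If subjects who died are left out, the comparison conditions on something that happened after randomization, and the arm with more deaths loses its sickest members.

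Both routes help the arm with more deaths. If VIS410 lowered mortality, the main and sensitivity results could disagree only because of the exclusion, and the disagreement would be read as death skewing the AUC. This matters even in an exploratory trial, because the protocol uses the p-values to choose and order endpoints for Phase 3.

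**Working it through.** **Inputs.** Scores 1 to 7 are from SAP 9.1. The AUC rule is from SAP 9.2.1, which names both a daily sum and the linear trapezoidal rule; sums are used unless stated. Inclusion criterion 4 requires oxygen support, so the Day 1 score is at least 4. Arms have 40 subjects (SAP 2.1). The documents give no planning value for the AUC or for mortality, so there is no plan figure to reproduce, and all death counts and courses below are assumptions. Differences are VIS410 minus placebo; negative favors VIS410.

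**One subject: ventilated Days 1-2, death on Day 3, Day 1-14.**
- Death scored 7: 6 + 6 + 12×7 = 96.
- Death days dropped: 6 + 6 = 12.
- Death scored 6: 14×6 = 84.
- Best possible survivor (4 on Day 1, then 1): 4 + 13×1 = 17.
- Fast ward recovery (4, 4, 3, 2, 2, then 1): 15 + 9 = 24.

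With death days dropped, this death beats every possible survivor. The trapezoidal rule agrees: 6.0 against (4+1)/2 + 12 = 14.5. Over Days 1-7 the sum falls from 6 + 6 + 5×7 = 47 to 12, close to the best possible survivor (4 + 6 = 10). The effect belongs to early deaths: ventilation on Days 1-9 with death on Day 10 still sums to 9×6 = 54.

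**Dropping subjects who died, Day 1-7.** Assume 36 of 40 per arm average 22. Four placebo subjects die with an AUC of 46 (ventilated Days 1-3, dead from Day 4: 18 + 28). Their four VIS410 counterparts survive with AUC *s*.
- All subjects: (36×22 + 4*s*)/40 − (36×22 + 4×46)/40 = (*s* − 46)/10.
- Deaths excluded: (36×22 + 4*s*)/40 − 22 = (*s* − 22)/10.
- *s* = 38 (6, 6, 6, 5, 5, 5, 5): −0.8 becomes +1.6.
- *s* = 22: −2.4 becomes 0.

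The exclusion moves the difference by +2.4 whatever *s* is. The sign reverses only if *s* lies between 22 and 46.

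**Both readings, Day 1-14.** Assume 6 placebo and 2 VIS410 deaths on Day 3, scored as above, four patients saved by VIS410, and all other survivors at 32.

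| Saved patients' sum | Death = 7 | Death days dropped | Dead dropped | Death = 6 |
|---|---|---|---|---|
| 84 (ventilated throughout) | −1.2 | +7.2 | +5.5 | 0.0 |
| 32 (ward recovery) | −6.4 | +2.0 | 0.0 | −5.2 |

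First row: 4×(84−96)/40; 4×(84−12)/40; (34×32 + 4×84)/38 − 32; 4×(84−84)/40. The second row puts 32 in place of 84.

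**Simulation.** 4,000 two-arm trials, 40 per arm, Day 1-14 sum, two-sided t-test at 0.05 without strata. Assumed: 20% ventilated, deaths on Days 2-6, ventilated subjects who do not die ventilated for 6-14 days, and no treatment effect other than on mortality.

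| | Death = 7 | Death days dropped | Dead dropped |
|---|---|---|---|
| 15% vs 5% deaths: mean difference | −2.0 | +5.8 | +4.4 |
| VIS410 looks worse | 35% | 95% | 90% |
| VIS410 significantly worse | 1% | 37% | 21% |

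At 10% vs 2.5%, VIS410 looks worse in 40%, 88% and 80% of trials. At 15% in both arms all mean differences are within 0.05 of zero.

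**The case against.** The strongest reply is that the SAP never prescribes either exclusion. A reader might infer that it orders death days or dead subjects to be dropped; the text says neither, and the table shells are in a separate document that may give a rule. SAP 3.2 lists the endpoint as a mean AUC, and on a per-day mean over living days the Day 3 death scores 6.0 per day, which is not a good value. This stands as far as it goes: the rule is undefined. But 9.2.1 specifies a sum, and on that basis the two natural readings both mislead.

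Second, reversal is not inevitable. It needs unequal deaths and, when the dead are dropped, saved patients who remain sicker than the average survivor. The simulated saved patients stay ventilated for at least six days, which favors reversal. This stands.

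Third, the consequence is small. The main AUC keeps death at 7, and all-cause and attributable mortality are reported at Days 14, 28 and 56. P-values are informational, and an imbalance in deaths would be visible elsewhere in the report. This stands, and it limits the importance of the point. It does not make the sensitivity analysis able to answer its own question.

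Fourth, rescoring death as 6 is a partial test. It changes one point per death day, leaves the carried-forward block in place, and equates death with ICU ventilation: in the first table's ventilated case the benefit falls from −1.2 to 0.0. This also stands and should be stated with the result.

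**Conclusion.** The point holds as a defect in one sensitivity analysis. The exclusion rule is undefined, and on either natural reading an unscaled sum favors the arm with more deaths, so the result cannot show whether death skews the AUC. For an early death the distortion is large (96 becomes 12, below the best survivor's 17). At arm level, dropping the dead can erase a survival benefit (−2.4 to 0) or reverse it (−0.8 to +1.6), depending on how sick the saved patients stay. These figures rest on assumed deaths and courses. With equal death rates no bias was seen, and a late death after prolonged ventilation does not get a low AUC.

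A reader might go further and conclude that the exclusion will reverse a true benefit, or that the AUC or primary comparison is compromised. The documents do not support that: reversal is conditional, the main AUC retains death, and the Day 7 primary analysis does not use this step.

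**What to change.** Replace the exclusion sentence in SAP 9.2.1 with a rescoring analysis. Keep every MITT subject, carry the death score through Day 14 for all deaths, and rerun the AUC ANOVA with death scored 6 beside the main analysis at 7. The carry-forward must be written out, because SAP 9.1 provides it only for deaths before Day 7; a death on Days 7-13 could otherwise have no later scores to rescore. State that the analysis tests only the extra score given to death over ICU ventilation. Retitle Table 14.2.1.3 to match, and record the change from the protocol synopsis in SAP 16.1.

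The cost is a few lines of SAP text and programming, with no new data.
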